#### ***Definition of patient groups:***

- PAD IIa
- PAD IIb

***Definition of healthy control group:***

- no PAD previously known
- no diabetes mellitus previously known
- no chronic renal insufficiency previously known
- no symptoms of intermittent claudication
- ABI with values between 0.9 and 1.4 (screening examination before inclusion in the study)
- palpable foot pulses

**Inclusion Criteria**

- Patients with manifest PAD in stage II according to Fontaine or categories 1-3 according to Rutherford or healthy volunteers
- Adults (>18 years) who are able to give their consent

**Exclusion Criteria**

- Patients with PAD stage I, III and IV according to Fontaine or categories 0, 4, 5 and 6 according to Rutherford or healthy volunteers with diabetes mellitus, chronic renal failure, claudication symptoms, abnormal ABI or non-palpable foot pulses
- Underage persons
- Lack of written consent
- Safety concerns of the study physician (person with physical, mental or psychiatric conditions which, by the judgement of the study physician, would compromise the person's safety or the quality of the data, thereby rendering the person an ineligible candidate for the study)

**5.3 Randomization and Blinding**

Randomization is not applicable in the chosen study design. Investigators for angiography and CCDS are blinded to index test (MSOT) results. An independent reader blinded to angiographic TASC-classification and CCDS measures performs data analysis for index test (MSOT).

**5.4 Study Variables**

	Visit	Annotations
Index test (MSOT) 	X	Before and after exercise
Angiography 		Considered only if angiographic imaging already available in the electronic patient file due to routine diagnostics independently from this study and if less than 12 months to the date of index test; Evaluated by two independent examiners
CCDS 	X	Whether a flow-relevant stenosis is present in the examined vessels is decided by an independent reader
ABI 	X	
Clinical scores 	X	

**1 Index Test (MSOT):**

Signal levels for oxygenated hemoglobin (HbO2), deoxygenated hemoglobin (Hb), total hemoglobin, oxygen saturation and single wavelengths from 700nm to 1300nm in arbitrary units (a.u.)

**2 Angiography:**TASC II classification femoro-popliteal PAD:

## Type-A:

- *circumscribed stenosis ≤ 10 cm or closure ≤ 5 cm length*

## Type-B:

- *several hemodynamically relevant findings (stenoses or occlusions), each ≤ 5 cm*
- *single stenosis or occlusion ≤ 15 cm length, not involving the infrageniculate popliteal artery*
- *single or multiple findings in peripheral vascular occlusion to improve inflow for distal bypass*
- *heavily calcified occlusion ≤ 5 cm length*
- *single popliteal stenosis*

## Type-C:

- *multiple stenoses or occlusions with a total ≥ 15 cm vessel involvement, with or without severe calcification*
- *Recurrent stenoses or occlusions requiring treatment after two endovascular interventions*

## Type-D:

- *chronic total occlusion of the CFA or the SFA (>20 cm) with affection of the arteria poplitea*
- *chronic complete occlusion of the popliteal artery and proximal trifurcation*

TASC II classification aorto-iliac PAD:

## Type-A:

- *uni-/bilateral stenoses of CIA*
- *uni-/bilateral single stenosis ≤ 3 cm of EIA*

## Type-B:

- *≤ 3 cm stenosis of infrarenal aorta*
- *unilateral CIA occlusion*
- *single or multiple stenosis totaling 3-10 cm involving the EIA but not extending into CFA*
- *unilateral EIA occlusion not involving IIA or CFA*

## Type-C:

- *bilateral CIA occlusions*
- *bilateral EIA stenoses 3-10 cm long but not extending into CFA*
- *unilateral EIA stenosis extending into CFA*
- *unilateral EIA occlusion that involves the IIA and/or CFA*
- *heavily calcified unilateral EIA occlusion with or without involving IIA and/or CFA*

## Type-D:

- *infrarenal aortoiliacal occlusion*
- *diffuse disease involving aorta and both CIA requiring treatment*
- *diffuse multiple stenoses involving unilateral CIA, EIA and CFA*
- *Unilateral occlusion of both CIA and EIA*
- *bilateral occlusion of EIA*
- *iliac stenoses with AAA requiring treatment (not amenable to endograft placement or other lesions requiring open aortic/iliac surgery)*

Formed subgroups (aggregated TASC [aTASC]) combining TASC types according to severity and theoretical collateralization capability

## aTASC 1: Healthy aTASC Type:

- *In the absence of angiographic imaging in the HV and otherwise normal findings in the medical history, ABI, and CCDS, HV are classified as aTASC 1*
- *individuals with unremarkable radiological findings according to TASC in each of the aortoiliacal (AI), femoropopliteal (FP) and infrapopliteal (IP) levels*

## aTASC 2: aTASC type with good chances for collateralization:

- *due to mild findings in AI levels and any findings in FP levels which is considered a potential for collaterals through A. profunda branches.*

## aTASC 3: aTASC type with poor chances for collateralization:

- *all combination of AI and FP TASC patterns with theoretically poor chances for collateralization. Here severe findings at AI level are summarized because of poor collateralization capability via A. profunda branches.*

aTASC 1	aTASC 2	aTASC 3
combination of 1. no AI TASC findings 2. no FP TASC findings 3. no IP TASC findings	combination of 1. AI no TASC or TASC A/B 2. FP no TASC or TASC A/B/C/D 3. any IP TASC findings 4. at least TASC A/B in 1. or 2.	combination of 1. AI TASC C/D 2. FP no TASC or TASC A/B/C/D 3. any IP TASC findings

**3 CCDS:**

Morphological flow profile and PSV of A. femoralis communis and A. poplitea

**4 ABI:**

Assessment of ABI value	
no PAD	0.9-1.4
mild PAD	0.75-0.9
moderate PAD	0.5-0.75
severe PAD	<0.5
mediasclerosis	>1.4

**5 Clinical scores:**

Relative and absolute walking distance determined in 6MWT

Total achieved walking distance in the 6MWT

Subjectively perceived absolute walking distance in everyday life

Perceived PAD-specific quality of life (VASCUQOL-6 questionnaire)

Fontaine classification

I=No symptoms [not included in this study]

IIa=painless walking distance >200 m, IIb=painless walking distance <200 m

III=pain while resting [not included in this study]

IV=trophic disorder [not included in this study]

Rutherford classification

0=No symptoms [not included in this study]

1=mild claudication

2=moderate claudication

3=severe claudication

4=ischemic rest pain [not included in this study]

5=minor tissue loss (nonhealing ulcer, focal gangrene and diffuse pedal ischemia) [not included in this study]

6=major tissue loss (extending above transmetatarsal level, foot no longer salvageable) [not included in this study]

## 6 Determination of Sample Size

Statistical sample size calculation based on the results of the previous study (MSOT\_PAD, NCT04641091) suggests a necessary study collective of at least 48 to a maximum of 124 subjects/patients. The two-sample t-test power calculation with a power of 0.8 gave an n of about 12 for each group (study group 1 - healthy volunteers, study group 1 - claudication patients, study group 2 - healthy volunteers, study group 2 - claudication patients). Additional sample size planning based on the AUC, which should be at least 0.7 for a relevant significance, gave an n of 31 subjects/patients for each group (with a significance level of 0.05 and a power of 0.8).

These calculations were based on data comparing healthy subjects with patients in stage IIb who, however, had not been adequately exercised (all only with the same walking distance of 150 meters). Due to the hypothesis of the study that the ability to differentiate between healthy subjects and claudication patients can be increased by adequate provocation testing, the sample size estimated here on the basis of the previous data is to be regarded as conservative. For this reason, after the inclusion of the first 25 patients and the first 25 healthy test persons, the necessary total sample size will be reevaluated in cooperation with the Institute for Biometry – on the basis of the data collected up to that point.

Dropout is not considered because the study is performed during a single visit.

## 7 General Considerations

### 7.1 Timing of Analysis

The final analysis will be performed after the last patient entered the study. Study collectives for study group 1 (derivation of thresholds) and study group 2 (validation of thresholds) will be handled separately.

### 7.2 Analysis Population

We will describe all screened and enrolled subjects who fulfil all inclusion criteria and fail all exclusion criteria.

### 7.3 Subgroups

Subpopulations are defined by the reference standard as follows: clinical according to Fontaine and TASC classification. If necessary and in order to confirm a flow relevant stenosis CCDS.

### 7.4 Missing Data

For the primary endpoint, single missing values will have no consequence. If missing, the individual subject will be excluded for the specific sub-analysis.

[figure not shown]

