In the end, after a resting pause of at least 15 minutes, a 6-minute walk test (6MWT) is performed in the hallway of the department of pediatrics. A course of 30 meters is marked, with additional markings every two meters. The participant is to walk as far as possible along this course (turning around every 30 meters) within six minutes. Breaks and changes of pace are allowed, but the patient is told that he should not take his first break until the claudication pain forces him to stop. That way, in addition to the total walking distance achieved within the six minutes, the actual maximum walking distance until the onset of claudication pain is recorded. In addition, the patient is asked to indicate the first occurrence of pain during the walking test, and the walking distance completed up to that point is also noted.

The time required for the CCDS and the three MSOT measurements, including the rest period prior to the start of the measurements, is approximately 60 minutes. These examinations take place exclusively in the context of study participation and are not part of routine diagnostics. Together with information and written consent, medical history, quality of life questionnaire and transport to the pediatrics department, the estimated time required for all procedures performed will be max. 90 minutes.

Afterwards, regardless of the results of the study measurements, the guideline-driven planned vascular surgical therapy will take place for the respective patient (endovascular treatment/vascular surgery, conservative procedure).

Figure 2 on page 13 shows the graphical representation of the planned measures, as well as their chronological sequence.

For the subgroup analysis, for which some of the included IC patients will be re-examined after revascularization intervention, the procedures described here will be performed again in exactly the same way. Only the anamnesis and the quality of life questionnaire can be omitted, reducing the total duration of the examinations by 15-20 minutes.

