- Correlation of the acquired MSOT parameters with the TASC-classification (angiography) [Time Frame: single time point (1 day)]: hemoglobin-associated MSOT parameters (units: arbitrary units (a.u.)) derived by transcutaneous MSOT in patients with IC correlated with the TASC-classification (angiography)  
[If angiographic imaging is already available due to routine diagnostics independently from this study.]
- Subgroup analysis: Difference between the corresponding MSOT values before and after revascularization intervention [Time Frame: two time points (2 days)]: Difference of the values before and after revascularization intervention for hemoglobin-associated parameters derived by transcutaneous MSOT in patients with IC
- Subgroup analysis: Reperfusion profiles of hemoglobin-associated MSOT parameters (i.e. the curves of hemoglobin-associated MSOT parameters in the first ten minutes after exercise) after revascularization intervention
- Subgroup analysis: Correlation of acquired MSOT parameters after intervention with the CCDS flow profiles and PSVs after intervention [Time Frame: single time point (1 day)]: hemoglobin-associated MSOT parameters (units: arbitrary units (a.u.)) derived by transcutaneous MSOT in patients with IC after revascularization intervention correlated with the flow profiles and PSVs of A. femoralis communis and A. poplitea determined by CCDS after revascularization intervention
- Subgroup analysis: Correlation of acquired MSOT parameters after intervention with the ABI after intervention [Time Frame: single time point (1 day)]: hemoglobin-associated MSOT parameters (units: arbitrary units (a.u.)) derived by transcutaneous MSOT after revascularization intervention correlated with the ABI measurements after revascularization intervention
- Subgroup analysis: Correlation of acquired MSOT parameters after intervention with relative (until the first occurrence of pain) and absolute walking distance (until the first stopping due to pain) determined during the 6MWT after intervention [Time Frame: single time point (1 day)]: hemoglobin-associated MSOT parameters (units: arbitrary units (a.u.)) derived by transcutaneous MSOT after revascularization intervention correlated with relative (until the first occurrence of pain) and absolute walking distance (until the first stopping due to pain) in the 6MWT after revascularization intervention

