MSOT MSOT values for oxygenated/deoxygenated/total hemoglobin, oxygen saturation and single wavelengths from 700nm to 1300nm Difference values ("deltas") between respective MSOT values before and after exercise	Mean $\pm$ SD Mean $\pm$ SD
Walking distances Relative walking distance in 6MWT (until first occurrence of pain) Absolute walking distance in 6MWT (until first stopping because of pain) Total walking distance in 6MWT (total walking distance within the 6 minutes)	Mean $\pm$ SD Mean $\pm$ SD Mean $\pm$ SD
Anamnestic values Subjectively perceived absolute walking distance in everyday life Score in VASCUQOL-6 questionnaire	Mean $\pm$ SD Mean $\pm$ SD

### 12.3 Data correlation PAD II patients in study groups 1 and 2

All MSOT parameters have two values: "PRE" means before exercise and "POST" means after exercise. If not explicitly mentioned, the following assumes the analysis of both values.

Parameters	Hbtot	HbO2	Hb	Difference HbO2/Hb	Oxygen saturation	Single wave-lengths from 700nm to 1300nm
Angiography TASC score	Correlation	Correlation	Correlation	Correlation	Correlation	Correlation
CCDS Morphological flow profile, relevant stenosis PSV	Correlation	Correlation	Correlation	Correlation	Correlation	Correlation

Clinical scoring ABI Absolute/relative walking distance Total walking distance in 6MWT	Correlation	Correlation	Correlation	Correlation	Correlation	Correlation
Anamnestic scoring Subjectively perceived absolute walking distance Score in VASCUQOL-6 questionnaire	Correlation	Correlation	Correlation	Correlation	Correlation	Correlation

## 12.4 Data correlation healthy volunteers in study groups 1 and 2

All MSOT parameters have two values: “*Pre*” means before exercise and “*Post*” means after exercise. If not explicitly mentioned, the following assumes the analysis of both values.

Parameters	Hbtot	HbO2	Hb	Difference HbO2/Hb	Oxygen saturation	Single wave-lengths from 700nm to 1300nm
CCDS Morphological flow profile, relevant stenosis PSV	Correlation	Correlation	Correlation	Correlation	Correlation	Correlation
Clinical scoring ABI Absolute/relative walking distance Total walking distance in 6MWT	Correlation	Correlation	Correlation	Correlation	Correlation	Correlation
Anamnestic scoring Subjectively perceived absolute walking distance Score in VASCUQOL-6 questionnaire	Correlation	Correlation	Correlation	Correlation	Correlation	Correlation

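### The plan does not say how a six-minute walk without pain or without a pain-forced stop is recorded, so the secondary analyses of relative and absolute walking distance may lose or understate the best walkers

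*SAP*

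**What the plan says.** Protocol 9.2 describes one walk: "The participant is to walk as far as possible along this course (turning around every 30 meters) within six minutes". The instruction is that "he should not take his first break until the claudication pain forces him to stop", and by this means "the actual maximum walking distance until the onset of claudication pain is recorded". The relative distance comes from the same walk, because "the patient is asked to indicate the first occurrence of pain during the walking test"; the metres covered by then are written down. The total distance is recorded for everyone. SAP 5.4 (Clinical scores) confirms that relative and absolute distance come from this test.

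The only rule for an absent value is in SAP 7.4: "If missing, the individual subject will be excluded for the specific sub-analysis". SAP 8.2 keeps a subject with single missing values in the full analysis population. SAP 8 summarises continuous variables by mean and standard deviation. SAP 9.1 offers differences in mean, Pearson or Spearman; Protocol section 11 names Spearman.

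Eligible patients include both Fontaine substages, defined in SAP 5.4 as "IIa=painless walking distance >200 m, IIb=painless walking distance <200 m". SAP 4.3 repeats the correlations at the second examination, including with "absolute walking distance (until the first stopping due to pain) in the 6MWT after revascularization intervention". Healthy volunteers must have no claudication symptoms (SAP 5.2). Even so, SAP 12.2 and 12.5 plan means of both pain-defined distances for them, SAP 12.4 plans correlations with MSOT, and SAP 12.5 lists both distances in a sensitivity and specificity table.

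**The concern.** Both distances are defined by an event, and the observation window closes after six minutes. A participant who walks the whole time without stopping has no absolute distance; one without pain has no relative distance. The information is not absent: the true value lies beyond the distance the participant reached.

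The plan has no event indicator, ceiling code or censored-data method. Staff could leave the field blank or enter the distance reached, and could do so differently from one another or between the two visits. A blank makes the sample depend on the outcome being correlated. An entered distance keeps the participant, but makes absolute distance identical to total distance for every non-stopper. It also lets a slow walker who never stopped rank below a faster one who did.

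The correlation with relative and absolute distance is a named secondary hypothesis (Protocol 5.1) and endpoint (SAP 4.3). For volunteers the planned cells have no defined content without a rule.

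**Working it through.** **1. The plan's own figures.** The documents give no sample size or power for these correlations. The one calculation that can be checked is the AUC sample size (SAP section 6): AUC 0.7 against 0.5, alpha 0.05, power 0.8, equal groups. With the Obuchowski-McClish variance, a = 1.414 × 0.524 = 0.742 and a² = 0.55:

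- V₁ = 0.0099 × e^(−0.275) × [(5 × 0.55 + 8) + (0.55 + 8)] = 0.145
- V₀ = 0.0099 × 16 = 0.158
- n = (1.96√0.158 + 0.842√0.145)² / 0.2² = 30.3, so 31 per group (two-sided)

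This matches the plan. It implies at most 2 × 31 = 62 claudication patients; the t-test figure implies 2 × 12 = 24.

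**2. Can the six-minute limit bind?** Covering 200 m in 360 s needs 200/360 = 0.56 m/s. At assumed speeds of 0.8, 1.0 and 1.2 m/s the walk ends at 288, 360 and 432 m. Stage IIa has no upper limit on pain-free distance, so it can. The documents do not say how often.

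**3. Illustration with assumed walking data.** All inputs are assumptions: lognormal pain-stop distance (log SD 0.6), independent six-minute capacity with mean 380 m and SD 60 m, true Spearman about 0.38, 50 patients. The non-stopper share can be checked by hand: with a median of 300 m and the cap fixed at 380 m it is 1 − Φ(ln(380/300)/0.6) = 1 − Φ(0.39) = 35%, and 36% once capacity varies.

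| Median stop distance | 200 m | 300 m | 400 m |
|---|---|---|---|
| Non-stoppers | 15% | 36% | 54% |
| Correlation: excluded | 0.32 | 0.28 | 0.25 |
| Correlation: distance reached | 0.37 | 0.34 | 0.29 |
| Correlation: top tied rank | 0.38 | 0.36 | 0.34 |
| Power: excluded | 0.54 | 0.32 | 0.19 |
| Power: distance reached | 0.78 | 0.69 | 0.53 |
| Power: top tied rank | 0.78 | 0.75 | 0.68 |

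Repeat runs differ by up to about 0.03 in power.

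**4. Means.** At a median of 300 m the true mean is 300 × e^(0.6²/2) = 300 × 1.197 = 359 m. The expected reported mean is 279 m with distance reached (80 m too low) and 232 m with exclusion (127 m too low).

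**5. A second model.** Bivariate normal data, true correlation 0.4, 62 patients, with the top fraction event-free. With nobody event-free, mean Spearman is 0.37 and power 86%.

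| Event-free | 10% | 30% | 50% |
|---|---|---|---|
| Excluded: correlation, power | 0.33, 71% | 0.27, 44% | 0.22, 24% |
| Top tied rank: correlation, power | 0.38, 88% | 0.37, 85% | 0.35, 80% |

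With 24 patients and 30% event-free, power is 20% with exclusion and 43% with top rank.

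**The case against.** A reader might infer that participants who never stop are dropped as missing. The documents do not say so: SAP 7.4 states what happens if a value is missing, and no section classes a completed pain-free walk as missing. The planned volunteer means in SAP 12.2 and 12.5 fit the other reading at least as well, since people without claudication have a mean only if some number, such as the distance reached, is entered. On that reading most of the power loss disappears. If capacity and pain-stop distance are also correlated (assumed 0.5), power with distance reached is 0.77, 0.73 and 0.65, against 0.77, 0.74 and 0.68 for top rank. This part of the objection stands.

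Nor do the documents support saying that event-free walks will be common. The 200 m limit concerns first pain rather than stopping, and the IIa/IIb mix is not given.

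It is also too strong to say that the revascularization subgroup is reduced to treatment failures. Even under exclusion, only the correlations and summaries of these two distances lose patients. The before-and-after MSOT differences, the reperfusion profiles and the correlation with total six-minute distance keep every treated patient.

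Finally, tied top ranks are not free of error: a non-stopper who covered 280 m is placed above a patient who stopped at 350 m, although that order is not established.

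What the objection does not remove is the gap. Two conventions are open, they give different results, and both understate the mean.

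**Conclusion.** The concern holds as a missing rule for recording and analysing event-free walks. Exclusion is the consequence only if the field is left blank; entering the distance reached is milder for the correlation but still biases mean ± SD downward.

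The size is conditional. In the illustration exclusion takes power from 0.54 down to 0.19 as non-stoppers rise from 15% to 54%, and distance reached from 0.78 to 0.53. Those shares follow from assumed walking distances. The volunteer cells need no such assumption: without a rule they are undefined for nearly everyone.

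The reach is limited to the secondary correlations and summaries of relative and absolute distance at both visits. The primary MSOT threshold analysis, total six-minute distance and perceived everyday walking distance are unaffected. The change should be made, because an event-free walk not recorded as such may not be recoverable later, but it does not threaten the main result.

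**What to change.** - **Definition (SAP 7.4 and 9.1).** State that no pain, or no stop, within six minutes is a right-censored result and not a missing value.
- **Recording.** For each of the two distances, add a yes/no event field and record the distance reached.
- **Correlation.** Use Spearman for these distances, with event-free participants at the top tied rank. Add a censored-data rank correlation as a sensitivity analysis, because of the ordering problem noted above.
- **Summary.** Report the median and the percentage censored by group and visit in place of mean ± SD. If the median is not reached, say so.
- **Second examination.** Apply the same rule after revascularization.
- **Healthy volunteers.** Report the percentage event-free, and drop the within-volunteer means and correlations of these two distances in SAP 12.2, 12.4 and 12.5. Keep the censored values for the sensitivity and specificity table in SAP 12.5, which needs them.

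The cost is a few sentences in the SAP and the event fields on the walk-test form. No procedure, eligibility criterion or sample size changes. Tied ranks carry slightly less information than exact distances, and mean ± SD is given up for these two variables.
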